11.4 Randomization Visit: Visit 3 (Day 17)

Following at least 2 weeks wash-out period, eligible subjects will return to the clinic for Visit 3 to participate in the treatment periods.

- Verification of Subject ID.
- Clinic staff will update the subjects' concomitant medication and collect AEs and vital signs (blood pressure, heart rate, oral temperature and respiratory rate).
- Eligibility criteria will be reviewed.
- Diary cards including asthma action plan will be collected and reviewed and subjects will be issued a new diary.
- Asthma control questionnaire will be completed.
- A urine pregnancy test will be performed (for all WOCBP). Subjects with a positive result will be excluded (see Clinical Laboratory Tests Section 12.2.1)
- Subjects will be randomized to either Sequence treatment AB or Sequence Treatment BA.
- Subjects will be dispensed ADX-629 or placebo for at-home treatment. Subjects will be instructed to take the treatment orally twice per day (refer Section 10.1 for detail

dosing instructions) and return to the Clinic for the Post-Treatment Period 1. Subjects will receive their first dose on-site.

- Subjects will continue to keep a daily log of any changes in their health or medication use (including rescue medication) and time of dosing in their new diary while at home. They will also continue to refer to the asthma action plan, if there is any worsening of asthma control.
- Blood sample will be collected for PK assessment at 1 hour (+5 minutes) post dose.
- ECG will be performed at 1 hour (± 15 minutes) post dose.

11.5 Treatment Period 1 (Day 17 to Day 23 [+3])

- At home, subjects will take the treatment (Treatment A or Treatment B) orally twice per day i.e. PO bid dosing for minimum 1 week (+3 days) and return to the Clinic for the Post-Treatment Period 1. Subjects will take the morning and evening dose at the same time each day.
- Subjects will continue to keep a daily log of any changes in their health or medication use (including rescue medication) and time of dosing in their diary while at home. They will also continue to refer to the asthma action plan, if there is any worsening of asthma control.

11.5.1 Reminder Phone Calls - Treatment Period 1

- There will be a phone call during the treatment period 1 to follow up on subject's health and treatment compliance.
- Additionally, subjects will receive a phone call on the last day of the treatment period to remind them that their morning dose (600 mg) of the treatment will be administered onsite next day.

11.6 Post-Treatment Period 1 (2 consecutive days): Visits 4a and 4b (Day 24 and 25)

- Subjects will not stop treatment in order to maintain steady state concentration of the drug during the **Visits 4a and 4b**. Hence subjects will continue to receive their respective treatments with same schedule. However, on the days of visits 4a and 4b, subjects will receive their morning dose (600 mg) of the treatment on site approximately one hour prior to MCT or BAC.
- Verification of Subject ID.
- Eligibility criteria will be reviewed.
- Diary cards including asthma action plan will be collected and reviewed and subjects will be issued a new diary.
- Staff will update the subjects' concomitant medication and collect AEs and vital signs (blood pressure, heart rate, oral temperature and respiratory rate).

- Staff will collect any remaining at home treatment (either at Visit 4a and/or 4b based on subject's decision regarding confinement). At Visit 4a, subject will be dispensed at home treatment, if applicable based on their decision regarding confinement.
- Asthma Control Questionnaire will be completed at Visit 4a.
- Blood and urine sample will be collected for safety clinical laboratory tests (CBC with differential, electrolytes [Calcium, Sodium, Potassium, Chloride], eGFR, creatinine, BUN, ALT, AST, ALP, total bilirubin, albumin, total protein, glucose, total cholesterol, triglycerides, lipase and amylase and urinalysis including assessment of microalbuminuria).
- At **Visit 4a**, pre-BAC FeNO (baseline) and baseline FEV₁ will be performed. Pre-BAC FeNO to be performed prior to baseline FEV₁. At approximately 1 hour post-dose blood samples will be taken and sent to analytical lab for exploratory biomarkers (RASP and endotoxin-induced cytokine release) prior to BAC. An additional blood sample will be collected for PK assessment at 1 hour (+5 minutes) post dose. An ECG will be performed at 1 hour (\pm 15 minutes) post dose.
- Subjects will undergo BAC with the target allergen titer dilution identified in the pre-treatment allergen challenge visit (Visit 2b). Approximately 7 h post-BAC, FeNO will be measured (see Section 12.1.6) and then sputum will be induced, collected, and processed. FeNO to be performed prior to 7 h FEV₁ measurements. Additionally, blood samples will be taken and sent to analytical lab for exploratory biomarkers (RASP and endotoxin-induced cytokine release), at approximately 7 h post-BAC. The subjects will be given the option to be confined at the study site in order to facilitate early morning visit on the next day.
- Once all procedures are completed, subjects will be reminded to take their next day morning dose on site approximately one hour prior to MCT.
- The following day (Visit 4b), subjects will undergo post-BAC, MCT, FeNO and sputum testing (approximately 24 h post-BAC). FeNO will be performed before any other procedure on Visit 4b. Procedures for MCT (including baseline FEV₁) will be repeated as described in Visit 2a, except that the maximum concentration of Mch used in this visit will be up to 16 mg/mL. Following the MCT, sputum will be induced, collected, and processed (approximately 24 h post-BAC) (see Section 12.1.7). After completion of **Visit 4b** study procedures, subjects will be dispensed the second treatment according to their assigned sequence and at-home diaries and will be asked to follow the same instructions as previously directed.
- Following Visit 4b, subjects will complete 2 weeks of washout period. Subjects will continue to keep a daily log any of any changes in their health or medication use (including rescue medication) and time of dosing in their new diary while at home. They will also continue to refer to the asthma action plan, if there is any worsening of asthma control.

11.7 Treatment Period 2 (2 weeks after Visit 4b) (Day 39 to Day 45)

- At home, subjects will take the treatment (Treatment B or Treatment A) orally twice per day i.e. PO bid dosing for minimum 1 week (+3 days) and return to the Clinic for the Post-Treatment Period 2. Subjects will take the morning and evening dose at the same time each day.
- Subjects will continue to keep a daily log of any changes in their health or medication use (including rescue medication) and time of dosing in their new diary while at home. They will also continue to refer to the asthma action plan, if there is any worsening of asthma control.

11.7.1 Reminder Phone Calls - Treatment Period 2

- Subjects will receive a phone call approximately 1 day prior to their scheduled initiation of at-home dosing as a reminder to start treatment. Staff will update the subjects' concomitant medication and rescue medication use and collect AEs.
- There will be a phone call during the Treatment Period 2 to follow up on subject's health and treatment compliance.
- Additionally, subjects will receive a phone call on the last day of the treatment period to remind them that their morning dose (600mg) of the treatment will be administered onsite next day.

11.8 Post-Treatment Period 2 (2 consecutive days): Visits 5a and 5b (Day 46 & 47)

- Subjects will return to the Clinic for the Post-Treatment Period 2 following approximately 3 weeks (+3 days) later after having completed 2 weeks of washout and 1 week (+3 days) of at-home dosing.
- At **Visits 5a and 5b**, subjects will follow same procedures as performed previously at Visits 4a and 4b, respectively. As with Visits 4a and 4b, on the days of visits 5a and 5b, subjects will receive their morning dose (600 mg) of the treatment on site approximately one hour prior to MCT or BAC.
- Additionally, at Visit 5b, paper diary cards including asthma action plan and any remaining at home treatment will be collected from the subjects and a urine pregnancy test will be administered to WOCBP.
- Subjects will complete a health check prior to clinical trial exit.

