8. CLINICAL TRIAL DESIGN

ADX-629-AA-001 is double-masked, cross-over, placebo-controlled, single center, randomized clinical trial to assess the clinical safety and efficacy of ADX-629 compared to placebo in mild cat or HDM-induced asthmatics using the BAC model. The study will consist of 9 visits to the clinic (Visits 1, 2a, 2b, 2c, 3, 4a, 4b, 5a, and 5b) over a period of approximately 75 days (Please refer study design section 5.2). During this period there will be 4 additional visits, 1 visit for safety lab and 3 visits for COVID-19 testing, as described below. The clinical trial will be conducted as follows:

1. Medical Screening: Visit 1
2. COVID-19 test within 5 days prior to Pre-Treatment Period
3. Pre-Treatment Period (For 3 consecutive days)
 - i. Visit 2a
 - ii. Visit 2b
 - iii. Visit 2c
4. Washout (2 weeks)
5. Additional visit for safety sample blood collection within 3 days of Visit 3
6. Randomization Visit: Visit 3
7. Treatment Period 1 (at home treatment taken for 1 week [+ 3 days])
8. COVID-19 test prior to Post-Treatment Period 1
9. Post-Treatment Period 1 (For 2 consecutive days):
 - i. Visit 4a
 - ii. Visit 4b
10. Washout (2 weeks)
11. Treatment Period 2 (at home treatment taken for 1 week [+ 3 days])
12. COVID-19 test prior to Post-Treatment Period 2
13. Post-Treatment Period 2 (For 2 consecutive days):
 - i. Visit 5a
 - ii. Visit 5b

A re-screening visit will be included to the subjects who failed under previous versions of the Protocol.

The end of study is defined as the time at which the last subject has completed all study procedures in the clinical trial. Upon completion of the clinical trial, the study product will no longer be available to the subject but the Investigator can, at their discretion, discuss alternative treatments with the subject.

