9. SUBJECT SELECTION

9.1 Number of Subjects

Enough subjects will be enrolled to ensure approximately 12 subjects complete the study.

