12.2.6 Paper Diaries

During the study, each subject enrolled will be issued a paper diary including asthma action plan at Visits 2a, 2b, 2c, 3, 4a, 4b, and 5a, to collect the following at-home information as per Schedule of Assessments (see Section 5):

- AEs (pre-treatment and post-treatment)
- Disease symptoms
- Concomitant medication use

Paper diaries will be collected and reviewed at Visits 2b, 2c, 3, 4a, 4b, 5a, 5b, and ETV.

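### In the visible text, no contact asks completers about new adverse events once they leave after Visit 5b, the day of the last Period 2 dose

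*Protocol*

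**What the plan says.** **After the last Period 2 dose.** Protocol 11.8 has subjects take the Visit 5b morning dose on site about one hour before the methacholine challenge. SAP 5.4 treats that dose as completing treatment. At Visit 5b "paper diary cards including asthma action plan and any remaining at home treatment will be collected from the subjects", and 11.8 adds "Subjects will complete a health check prior to clinical trial exit". The clinic visits listed in Section 8 end at 5b. Under 12.2.6 each subject is "issued a paper diary including asthma action plan at Visits 2a, 2b, 2c, 3, 4a, 4b, and 5a", so none is issued at 5b. The last call in 11.7.1 falls on the day before Visit 5a.

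**After the last Period 1 dose.** Section 11.6 says "Following Visit 4b, subjects will complete 2 weeks of washout period", with a daily health and medication log at home. About one day before Period 2 dosing, staff phone each subject to update "concomitant medication and rescue medication use and collect AEs" (11.7.1).

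**At the visits themselves.** Under 11.6 staff update "concomitant medication and collect AEs and vital signs" at Visits 4a and 4b. Section 11.8 repeats those procedures at 5a and 5b.

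**Other provisions.** AEs already present are followed until they resolve or settle (17.2.1). Early terminators are queried at the early termination visit, if possible (11.9). The 24-hour limit for reporting serious AEs runs from the investigator's awareness (17.2.2). The 30-day notice asked of subjects concerns pregnancy only (17.1.1).

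**The concern.** AEs and serious AEs are the endpoint for the primary objective (7.1, 7.2). Subjects leave after Visit 5b with drug probably still in the body, one day after an allergen challenge and shortly after a methacholine challenge and sputum induction. They no longer hold the diary or the action plan that tells them when to call the site. A new event at home then reaches the site only if the subject volunteers it, and an event that nobody asked about cannot be recovered at analysis. The plan does ask after Period 1 and gives no reason for the difference.

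**Working it through.** **1. The plan's own duration.** Screening starts at the earliest on Day -28 (11.2) and Visit 5b is Day 47 (11.8). 28 + 47 = 75 days, which matches the stated figure of about 75. If both +3-day windows are used, 75 + 6 = 81. A call on day 3 would end at 28 + 50 = 78. The count therefore argues against a long follow-up but cannot exclude a short call.

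**2. The two periods side by side.**

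| | After the Visit 4b dose | After the Visit 5b dose |
|---|---|---|
| AE collection during the visit | Yes | Yes |
| Diary at home afterwards | Yes, issued at 4b | None issued |
| Later call that asks about AEs | Yes, before Period 2 dosing | None in the visible text |
| Follow-up of AEs already present | Yes | Yes |

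On the nominal calendar the Period 1 follow-up runs from Day 26 to Day 38, which is 13 days.

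**3. Who is affected.** There are 6 subjects per sequence (10.2), and Section 9.1 aims to "ensure approximately 12 subjects complete the study". Sequence AB has follow-up at home after ADX-629 but not after placebo; BA has the reverse. So 6 of about 12 completers lack it on each treatment.

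**4. How long drug exposure lasts.** Half-lives are from 6.5: 4.56 h on Day 10 at 600 mg twice daily, with multiple-dose means of 3.07 to 6.20 h.
- Five half-lives: 5 × 3.07 = 15.4 h; 5 × 4.56 = 22.8 h; 5 × 6.20 = 31.0 h.
- The exit time is not given. Assume exit 2 to 6 h after the dose and first-order decay from dosing, so the fraction left is 2^(-t/half-life). At 4.56 h this is 2^(-2/4.56) = 74% down to 2^(-6/4.56) = 40%. The extremes are 2^(-2/6.20) = 80% and 2^(-6/3.07) = 26%.
- Most of that range was already passed through at home under a diary. With an assumed 12 h dosing interval, each dose falls to 2^(-12/4.56) = 16% before the next (7% to 26% over 3.07 to 6.20 h). Only the tail below that level is new: 22.8 - 12 = 10.8 h at 4.56 h, and 3.4 to 19.0 h over the range of means.

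**5. What one call would add.** Day 3 is 72/6.20 = 11.6 half-lives at the longest mean.
- Queried person-days over 3 days after the last ADX-629 dose are 6 × 3 = 18 now and 12 × 3 = 36 with the call. The 18 leaves out on-site time in BA. At the assumed 2 to 6 h, that adds 6 × 2/24 = 0.5 to 6 × 6/24 = 1.5 person-days. Placebo gives the same figures.
- If no such event is seen, the one-sided 95% upper limit for its risk is 1 - 0.05^(1/6) = 39% with 6 subjects and 1 - 0.05^(1/12) = 22% with 12.

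**The case against.** The strongest objection is that the absence cannot be confirmed. The Schedule of Assessments is not shown, and 12.2.5 ties AE queries to what is scheduled and to the investigator's direction. This stands and makes the point conditional. Exit on the day of Visit 5b is also an inference: 11.8 puts the health check before exit without naming a day.

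The practical value can also be questioned. The exposure tail is short, 6.5 reports no interruption or discontinuation in Phase 1, and no document predicts a delayed event. An upper limit of 22% instead of 39% excludes no small risk, and one recall call does not match a daily diary. All of this stands, and it keeps the point small. The investigator's on-call duty and the staff availability between periods (17.1) help, but neither is an active query of subjects who have left.

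Three stronger readings are tempting, and the documents do not support them.
- **A biased safety comparison.** With equal sequences, ADX-629 and placebo each lose follow-up at home in 6 subjects.
- **No observation after the last ADX-629 dose in sequence BA.** Visit 5b repeats the Visit 4b procedures, including AE collection, so the hours on site after the dose are covered in both sequences.
- **Late events lost through the SAP definition.** The treatment-emergent definition in SAP 7.2 has no end date, so a volunteered late event would still count. It does pool Period 1 washout events with on-drug events, but onset dates are recorded (17.2.1) and all AEs are listed, so these can be separated.

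**Conclusion.** The gap holds on the visible text and is a cheap improvement to consider. It is confined to new-onset events after completers leave following Visit 5b. It affects about half the subjects on each treatment and matters mainly over roughly the first day. It reduces the absolute post-dose safety information and leaves the treatment comparison intact. The conclusion assumes that the Schedule of Assessments holds no later call and that sequences complete in about equal numbers. The drug-remaining percentages also depend on the assumed exit time; the 15 to 31 h span does not.

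**What to change.** - **Protocol 11.8:** add one phone query on AEs, serious AEs and concomitant medication about 3 days after the last dose, for every subject. If the Schedule of Assessments already lists such a call, repeating it in 11.8 is enough.
- **Protocol 11.9:** add the same query about 3 days after early termination.
- **SAP 7.2 (optional):** tabulate events that start after each period's last dose in a follow-up window of equal length, for example 3 days. Period 1 needs no new contact, because the washout diary, the existing call and the onset dates supply the data.

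The cost is a small amendment, about 12 short calls by a site that already phones subjects, and about 3 more days of participation per subject. No new procedure is needed. Three days is a judgement based on the half-life; the documents set no follow-up length.

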11.9 Early Termination Visit (ETV)

The following procedures will be carried out following the premature withdrawal of any patient from the study, if possible:

- Paper diaries will be collected and reviewed.

- Any unused at home treatments will be collected.
- Patients will be queried for AEs and concomitant medication use.
- Asthma control questionnaire will be completed.
- Urine pregnancy test for WOCBP only, if not performed before on the same day.
- Vital signs (blood pressure, heart rate, oral temperature and respiratory rate) will be measured.

12. STUDY PROCEDURES AND SAFETY ASSESSMENTS

12.1 Study Procedures

12.1.1 Skin Prick Test (SPT)

At Visit 1 (Medical Screening Visit), subjects will undergo SPT.

In addition to the test allergens, positive controls and negative controls will be used during SPT challenge. A positive test is considered as ≥ 3 mm wheal compared to the negative control.

Skin Prick Test will be performed with a panel of test allergens (HDM [*Dermatophagoides pteronyssinus*, *Dermatophagoides fariniae*] or cat [*Felis domesticus*], mold, dog).

Skin Prick Test will be performed with a single prick device.

For detailed SPT procedure, refer to the site standard procedures.

12.1.4 Multi-skin Prick Sensitivity Test

At Visit 2a, those subjects who complete MCT and continue to be eligible to participate in the study will undergo a multi-skin prick sensitivity test. This test will employ similar procedures as SPT (see Section 12.1.1). However, multi-skin prick sensitivity test will be done using doubling concentrations of cat/HDM allergen extracts as shown in table below.

[figure not shown]
Preparation of serial dilutions using a single allergen solution

The wheal diameter will be measured as per the site standard procedures. Skin sensitivity will be defined as the lowest allergen concentration that produces a wheal of ≥ 3 mm in diameter relative to the negative control.

12.1.5 Bronchial Allergen Challenge (BAC)

Subjects will undergo BAC at Visit 2b, 4a, and 5a. Before the BAC can be performed, qualified personnel will explain the procedure and the expected symptoms to the subjects. The allergen concentration to be administered will be determined based on the results from the MCT and allergy SPT titrations performed at Visit 2a.

12.1.6 Fractional Exhaled Nitric Oxide (FeNO)

FeNO will be measured at Visit 4a, 4b, 5a and 5b at following timepoints:

- Pre-BAC at Visit 4a and Visit 5a
- Approximately 7 hour post-BAC at Visit 4a and Visit 5a
- Approximately 24 hour post BAC at Visit 4b and Visit 5b.

FeNO to be performed before FEV₁ measurements and sputum induction. The detailed technique for measurement of FeNO will be covered in site standard procedures.

12.1.7 Sputum Analysis

Sputum will be analysed for absolute count, percentage differential count of sputum eosinophils and neutrophils. Sputum will be induced, collected, and processed

- Approximately 7 hour post-BAC at Visit 2b, Visit 4a and Visit 5a,
- Approximately 24 hour post BAC at Visit 2c, Visit 4b and Visit 5b.

The detailed technique of sputum collection and analysis will be covered in site standard procedures.

12.1.8 Biomarkers

Blood sample will be taken and sent to analytical lab for exploratory biomarkers (RASP and endotoxin-induced cytokine release) to be performed at an independent laboratory. Additional details regarding sample processing will be provided in separate lab manual.

Blood samples for biomarkers will be collected at following timepoints:

- Baseline at Visit 2c,
- Per-BAC at Visit 4a and Visit 5a (approximately 1 hour post dose) and
- Approximately 7 hour post-BAC at Visit 4a and Visit 5a.

12.2 Safety Assessments

Safety measurements may be obtained at the discretion of the Investigator in addition to the safety assessments described in this section.

12.2.1 Clinical Laboratory Tests

List of clinical laboratory tests that will be performed at Medical Screening Visit and within 3 days prior to the first dose of study drug is provided below. Additional tests performed at Visit 4a and 5a are also mentioned in the table with asterisk.

CBC with Differential*	Clinical Chemistry	Urinalysis*

• Hemoglobin• Hematocrit• White blood cell count with differential• Red blood cell count• Platelet count	
• Blood Urea Nitrogen*• Creatinine *• eGFR to be reported*• Total bilirubin*• Alkaline phosphatase*• AST (also known as SGOT)*• ALT (also known as SGPT)*• Glucose*• Albumin*	
• pH• Specific gravity• Protein• Glucose• Ketones• Bilirubin• Blood• Nitrates• Leukocyte esterase

CBC with Differential*	Clinical Chemistry	Urinalysis*
	
• Total protein*• Electrolytes (Sodium, Potassium, Chloride, Calcium)*• Lipase*• Amylase*• GGT• CPK• Total cholesterol*• Triglyceride*• TSH	
• Microalbuminuria assessment*• Microscopic urine analysis will be done if blood, nitrite and/or leukocyte esterase are present in the chemical urinalysis.

* Will be repeated at Visit 4a and Visit 5a

Urine sample for a pregnancy test will also be collected for WOCBP at Medical Screening Visit, within 3 days prior to the first dose of study drug, at Visit 3, Visit 5b, and ETV.

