5. STUDY SCHEMATIC

5.1 Schedule of Assessments

[figure not shown]

**CLINICAL STUDY PROTOCOL
C2D00212/ ADX-629-AA-001
Aldeyra Therapeutics, Inc**

CONFIDENTIAL

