10.3 Masking and Unmasking

10.3.1 Masking

This is a double-masked clinical trial. Investigators, qualified site personnel (except pharmacy staff), and subjects will be masked to the investigational product administered. The Sponsor will also be masked to the IP administered until database lock. Only the pharmacy staff and Scientific Affairs staff involved with preparing the randomization will have access to the treatment under evaluation.

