12.2.1.1 COVID-19 Test (SARS-CoV-2)

Within 5 days of study Visits 2a, 4a and 5a a nasal/nasopharyngeal/oropharyngeal swab will be collected at the clinical site for SARS-CoV-2 testing. Subjects with a positive test result will be excluded/withdrawn from the study.

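### In the visible text no pregnancy test is scheduled between Visit 3 and Visit 5b, so women in sequence BA start ADX-629 at home 22 to 25 days after their last scheduled test

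*Protocol*

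**What the plan says.** Protocol Section 12.2.1 gives the list of urine pregnancy tests for WOCBP: "at Medical Screening Visit, within 3 days prior to the first dose of study drug, at Visit 3, Visit 5b, and ETV". The visit descriptions in Sections 11.2, 11.4, 11.8 and 11.9 agree with it, except that they do not separately name the test within 3 days before first dose. The synopsis matches them.

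Section 11.6 lists no pregnancy test at Visits 4a and 4b, although urine is taken there: "Blood and urine sample will be collected for safety clinical laboratory tests". Section 12.2.1 places that repeat urinalysis at Visit 4a. The second treatment is dispensed once the Visit 4b procedures are complete. Dosing then starts at home after a two-week washout.

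The only contact planned just before Period 2 is a reminder call (Section 11.7.1), about a day ahead: "Staff will update the subjects' concomitant medication and rescue medication use and collect AEs". For Visits 5a and 5b, Section 11.8 says "subjects will follow same procedures as performed previously at Visits 4a and 4b, respectively", and adds a pregnancy test at Visit 5b only.

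The heading "5.1 Schedule of Assessments" is present, but the table under it is not shown.

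**The concern.** The protocol tests shortly before first dosing and again at Visit 3. In a crossover those tests protect the first period only. Subjects in sequence AB meet ADX-629 straight after them. Subjects in BA meet placebo then, and meet ADX-629 about three weeks later with no new scheduled test.

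Suppose a BA subject is pregnant at her first active dose, does not suspect it, and stays in the trial. The first scheduled test that could show it is at Visit 5b, the last dosing day. By then she would have taken almost the whole ADX-629 course and undergone another allergen challenge ("Subjects will undergo BAC at Visit 2b, 4a, and 5a"). The protocol itself treats fetal exposure as a concern: Section 17.1.1 withdraws a subject with a confirmed pregnancy and follows it to its end.

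**Working it through.** **Inputs.** Visit 3 is Day 17 (Section 11.4). Period 1 lasts 7 days, with up to 3 more allowed (11.5). Visit 4b is the day after Visit 4a (11.6). Washout is 2 weeks (11.6). Period 2 lasts 7 days, with up to 3 more (11.7, 11.8). Visit 5b is the day after Visit 5a. Washout is taken as exactly 14 days.

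**Reproducing the plan's own date.** Visit 4a = 17 + 7 = Day 24. Visit 4b = Day 25. Period 2 start = 25 + 14 = Day 39, as Section 11.7 states. With the extra 3 days in Period 1, the dates are Day 27, Day 28 and Day 42.

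**All window combinations.**

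| Extra days, Period 1 / Period 2 | Period 2 start | Visit 3 to start | Visit 5b | Visit 3 to Visit 5b |
|---|---|---|---|---|
| 0 / 0 | Day 39 | 22 days | Day 47 | 30 days |
| 0 / 3 | Day 39 | 22 days | Day 50 | 33 days |
| 3 / 0 | Day 42 | 25 days | Day 50 | 33 days |
| 3 / 3 | Day 42 | 25 days | Day 53 | 36 days |

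**Does the test within 3 days of first dose cover Period 2?** No. Section 8 ties the extra safety-sample visit to Visit 3 and lists no clinic visit between Visit 4b and the start of Period 2. Where the protocol means each period it says so, as in the dietary rows of the Section 9.3.2 table. Section 12.2.1 has no such wording.

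**Period 2 doses taken before the Visit 5b test.** Twice-daily dosing for 7 days plus Visit 5a gives 7 × 2 + 2 = 16. With 10 days it gives 10 × 2 + 2 = 22. If the test follows the Visit 5b morning dose, the counts are 17 and 23. The order is not stated.

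**Other contacts before or early in Period 2.**
- Eligibility review at Visits 4a and 4b: the last is 39 − 25 = 14 days before dosing (42 − 28 = 14 with the window).
- Reminder call: on Day 38 or 41, when the Visit 3 test is 38 − 17 = 21 or 41 − 17 = 24 days old.
- COVID-19 swab: "Within 5 days of study Visits 2a, 4a and 5a a nasal/nasopharyngeal/oropharyngeal swab will be collected at the clinical site". The earliest day is 46 − 5 = Day 41, which is 2 days after the first Period 2 dose.
- Visit 5a: 46 − 39 = 7 to 49 − 39 = 10 days after dosing starts.

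None of these is a scheduled pregnancy test.

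**Effect of an added test.** Visit 4a to Period 2 start is 39 − 24 = 42 − 27 = 15 days. A home test reported at the reminder call leaves about 1 day.

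**The case against.** The strongest reply is that this is a preference, not an error. The documents set no maximum interval between test and dose, require no test before each period, and do not call 22 to 25 days too long. By Period 2 a WOCBP has three scheduled negative tests behind her. She has used one highly effective or two effective contraceptive methods since at least 4 weeks before Screening (Sections 9.2 and 9.3.3). Exclusion 11 covers pregnancy and inadequate contraception, and eligibility is reviewed at Visits 4a and 4b, before the second supply is handed over. She must report a suspected pregnancy at once, and Section 12.2 lets the investigator add safety measurements. All of this stands, and it is why the risk is probably low. It does not supply a test: the last eligibility review is 14 days before dosing, and self-report needs suspicion.

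The missing Section 5.1 table is also a fair objection. The explicit list in Section 12.2.1 makes an extra test there unlikely, but not impossible.

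A reader might go further and infer that the protocol breaks its own pre-dose testing rule. It does not: that rule refers to the first dose of study drug, which is given at Visit 3 and is preceded by tests. A reader might also infer that both sequences are equally exposed, or that an added test would prevent drug exposure in both. In AB, Period 2 is placebo, so the test averts no ADX-629 exposure. It only detects a pregnancy earlier and spares placebo doses and further challenges.

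**Conclusion.** The point holds as a cheap subject-protection improvement. On the visible text, WOCBP in sequence BA start ADX-629 at home 22 to 25 days after their last scheduled test, and the next one comes 30 to 36 days after Visit 3. No stated rule is broken, and no endpoint or analysis is affected.

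This rests on Section 5.1 containing no further test, a washout of exactly 14 days, and the stated 3-day windows; a longer delay would widen the gap. The number of WOCBP is not given. With 6 subjects per sequence, as in SAP Section 2.3.1, it could be 0 to 6 in BA. It could be higher, because Protocol Section 9.1 enrolls enough subjects for about 12 to complete.

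**What to change.** **Main change.** Test the urine already collected at Visit 4a in all WOCBP, and require a recorded negative result before the second treatment is dispensed at Visit 4b. In Section 12.2.1, insert *Visit 4a (negative result required before the second treatment is dispensed at Visit 4b)* between Visit 3 and Visit 5b. Make matching edits in Section 11.6, the synopsis and Section 5.1. If Section 5.1 already shows such a test, only the text needs correcting. A confirmed positive falls under Section 17.1.1. Because "Investigators, qualified site personnel (except pharmacy staff), and subjects will be masked to the investigational product administered", the test must be given in both sequences. The gap falls to 15 days.

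**Optional addition.** Dispense a home urine test at Visit 4b, with the result reported at the existing call about 1 day before Period 2 (Section 11.7.1). Dosing starts only after a recorded negative; a positive means no dosing and a confirmatory test at the site. The gap falls to about 1 day. This step is more debatable, because the result is self-reported and unsupervised yet controls dosing.

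**Cost.** One strip per randomized WOCBP, or two with the home test. If exactly 12 subjects were randomized and all were WOCBP, that is 12 or 24 strips; more are possible for the enrollment reason above. Add a minor amendment (Section 20.4 asks for a signed formal document) with IRB notification under Section 20.1, and an occasional false positive that delays Period 2.
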